6. CONCOMITANT AND DISALLOWED MEDICATIONS

Subjects will be required to have been on first-line BTK inhibitors for at least 3 months at study start. Prior dose reductions for toxicity will be allowed.

Subjects will not be asked to discontinue any medication to participate in the study. However, prior use of other medications designed to treat specifically CLL or WM (i.e. venetoclax) will not

be allowed. Change in medication as determined by treating oncologist will be allowed.

Other vaccination will be allowed during the study provided it does not interfere with the study assays. Administration of another inactivated vaccine (for example influenza or pneumococcal vaccine) will only be authorized outside that critical time period that ranges from 7 days prior to the first dose until 7 days post-second dose. We will encourage patients to receive the influenza vaccine and come back for the study protocol 7 days later should this interfere with our study.

7. SUBJECT WITHDRAWALS

Subjects will be advised in the written informed consent forms that they have the right to withdraw from the study at any time without prejudice. Withdrawal of consent can be submitted to any member of the research team, after which point no further data will be collected on these patients.

Subjects may be withdrawn by the investigator if they fail to present for the second dose of the vaccine or for the first control blood draws, or if they experience a severe adverse effect attributed to the first dose of the vaccine.

If therapy needs to be modified and subjects stop BTK inhibitor therapy between enrollment and their second vaccine dose, they will be offered the second dose and remain on study.

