1. PURPOSE OF THE STUDY AND BACKGROUND

1.1. Purpose of the study

Chronic lymphocytic leukemia (CLL) and Waldenstrom's macroglobulinemia (WM) are known risk factors for zoster reactivation, commonly called shingles. Although a recently FDA-approved recombinant, adjuvanted herpes zoster vaccine (Shingrix) is currently being offered to these populations, no study has specifically evaluated them in combination with BTK inhibitors.

The purpose of the study is to complete a single-arm trial evaluating if patients with CLL or WM, while on treatment with first-line BTK inhibitors, can achieve immunologic response to Shingrix. If effective, this will result in a new, well-tolerated shingles prevention strategy for these patients.

Primary objective:

- To measure the humoral immune response 4 weeks after the completion of vaccination with the Shingrix vaccine in patients \geq 50 years with CLL and WM receiving first-line treatment with BTK inhibitors.

Secondary objectives include:

- To measure the humoral immune response at 24 months after the completion of vaccination with the Shingrix vaccine in patients \geq 50 years with CLL and WM receiving first-line treatment with BTK inhibitors.
- To measure PBMC activation by ELISPOT and/or flow cytometry at 4 weeks and 24 months following vaccination with Shingrix, as a marker of cellular mediated immunity.
- To determine the rate of lymphoma progression while receiving BTK inhibitors.
- To correlate lymphoma progression while receiving BTK inhibitors and vaccine response at 4 weeks and 24 months following the vaccination.

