3. CHARACTERISTICS OF THE RESEARCH POPULATION

3.1. Subject Characteristics

a) Number of Subjects:

Target accrual is 30 evaluable CLL or WM subjects receiving treatment with BTK inhibitors. Assuming a 10% drop out rate, we aim to enroll a total of 33 subjects. Participants will be replaced in case of drop out or failure to receive the second dose of the vaccine. Failure to have blood drawn for baseline and/or 4 weeks after vaccination will also warrant replacement.

Subjects will not be replaced if they fail to present to the blood draw 24 months post-vaccination.

In the case of a change of therapy between the first and second dose of the vaccine (including the addition of rituximab), patients will remain on study and will not be replaced. Their data will be included in the estimates of vaccine response in the intent-to-treat analysis but excluded from sub-group analyses.

Based on data from the University of Rochester Cancer Center pharmacy, as of May 2018, 150 CLL and WM patients are on BTK inhibitor therapy and there are approximately 20 new cases per month. A local CLL database confirms those numbers and shows that a total of about 50 patients are on single-agent, first-line ibrutinib as of January 2018. No patient was identified while collecting this data, with respect to patients' confidentiality.

Patients who have started BTK inhibitors come to clinic about every 3 months for routine visits. Based on those numbers, we expect the recruitment of 33 patients to be feasible within 6 months.

b) Gender and Age of Subjects:

Subjects must be at least 50 years old to participate. Patients under 50 years old are excluded as per the label of the vaccine. It is anticipated that most subjects will be in their sixth or seventh decade given the age distribution of CLL²³ and WM.²⁴ There is no upper age limit if the patient meets the other inclusion criteria.

We expect that only a minority of subjects will be diagnosed with WM as compared to CLL because it is a much rarer disease, with only 1400 new cases diagnosed each year in the United States.^{25,26}

All genders are accepted. It is expected that there will be slightly more males than females included in the study as the male-to-female ratio in CLL is normally 1.3-1.7.²⁷ and about 60% of WM patients are males.²⁴

c) Racial and Ethnic Origin:

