5. METHODS AND STUDY PROCEDURES

Screening procedures will take place after subjects have consented to study participation.

Subjects will be asked to return to the clinic at a later date to have the baseline blood tests performed and the vaccine administered. We will determine a selection of dates where a certain number of patients will be able to have both procedures performed on the same day.

Blood may also be drawn for baseline testing at the Cancer Center and subjects subsequently administered the vaccine at the outpatient pharmacy on screening day.

After consent, a brief chart and CLL database review will be performed to collect certain variables such as those listed below:

- Age
- Stage at diagnosis
- Date of diagnosis
- 17p deletion (yes/no)
- TP53 mutation (yes/no)
- Mutated status of IVHG (yes/no)
- 11q del (yes/no)
- Presence of trisomy 12 (yes/no)
- Del 13q (yes/no)
- Watch and wait period duration
- Date of BTK inhibitor therapy initiation
- History of zoster reactivation

- History of zoster vaccination
- Immunoglobulin levels before study start
- Use of rituximab in the past (yes/no)
 - Number of cycles
 - Date of last cycle

Prior to the first dose of the vaccine, blood will be collected to assess immunity via measurement of anti-gE and cellular-mediated immunity. Samples will be processed in the cancer center research laboratory. Peripheral blood mononuclear cells (PBMC) will be processed and cryopreserved for future cellular assays and serum will be banked for analysis of anti-gE.

At visit 2, four weeks post-first dose, subjects will be contacted by phone call to report any adverse events. A chart review for severe adverse events will also be performed.

As per the label of the vaccine, the second dose of the vaccine will be administered two months after the first one, at visit 3. One month subsequent to that second dose, at visit 4, a second blood draw will be performed to evaluate the subject's immunogenic response. The initial analyses will be repeated, and response will be measured using statistical methods described below. Safety will be assessed again in the same way as after the first dose. A chart review will be performed to assess CLL/WM progression on BTK inhibitor therapy as determined by subjects' regular team of providers during their latest visit.

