These analyses will be repeated 24 months after the last dose of the vaccine to assess long term immunogenicity, at visit 5. A last chart review also be performed to assess incidence of zoster reactivation and disease progression as determined by their team of providers during the latest visit.

Table 1. Schedule of Study Procedures

Visit	Screen*	1*	2	3	4	5
		Dose 1	Safety assessment	Dose 2	Blood draw	Optional Blood draw
Visit window		0	Week 4 ± 1 week	Weeks 8-12	4 Weeks ± 1 week after Dose 2	24 months ± 3 months of Dose 2
Obtain informed consent	X					
Confirm eligibility	X					
Enroll	X					
Vaccine administration	X*	X*		X		
Lab work (anti-gE and CMI)	X*	X*			X	X
Safety assessment (patient-reported AEs)			X		X	

and chart review)						
-------------------	--	--	--	--	--	--

*Note: Administration of the first dose of the vaccine and completion of the lab assays will take place once, either at the screening visit OR at the first visit. If this is done at screening, then screening and visit one will happen within the same visit.

Subjects will be contacted through phone call OR in person at the clinic on for safety assessment.

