5.2. Efficacy Assessments

Vaccine response, as determined by blood antibody levels to the varicella virus glycoprotein E subunit (anti-gE), will be measured by ELISA. This humoral response will be assessed four weeks after vaccination is complete. In patients who were seropositive before the study, a positive response will be defined as at least a four-fold increase in geometric mean concentration (GMC) of anti-VZV gE antibody as measured per ELISA. Humoral response in seronegative patients at baseline will be defined as at least a four-fold increase from the lower detection limit of the anti-gE antibody assay.

Secondary efficacy objectives include:

1. Measure humoral response at 24 months post-vaccination, which is defined as persistence of anti-gE antibody above test threshold at 24 months.
2. Measure cell-mediated response to vaccination at one month and 24 months after vaccination.
3. Evaluation of CLL/WM progression on BTK inhibitor as determined by treating oncologist at latest assessment, and correlation between progression on BTK inhibitor and vaccine response at 4 weeks and at 24 months post-second dose.

Cellular-mediated response will be determined by measuring PBMC activation (by ELISPOT or flow cytometry) following stimulation with varicella glycoprotein E peptide. PBMC activation at 4 weeks and 24 months post dose will be compared to pre-vaccination activation levels.

a. Safety Assessments

Subjects will be educated to recognize immediate adverse reactions to the vaccine. Patient-reported signs of allergic or hypersensitivity reactions will be assessed and managed by the study team as needed. Only severe adverse effects will be captured in this study. Subjects will be contacted 4 weeks \pm 1 week after each dose of the vaccine for assessment and their chart will be reviewed at the same moment. Severe adverse effects are defined as any grades 3-5 adverse effects included in the CTCAE v5.0 classification.

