8.4. Subject Withdrawal of Study Drug

Subjects cannot continue to be followed in the study if they refuse to complete the vaccination process. However, the label of the vaccine specifies the second dose of the vaccine can be administered between 2 to 6 months subsequent to the first one. In that context, if subjects were to get the second dose within that period, they could still be included in the trial, provided data collection is still ongoing.

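### Subjects who do not complete vaccination or the visit-4 draw can leave the study with no chart follow-up, so progression and zoster reactivation may be estimated in completers only

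*Combined protocol and SAP*

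**What the plan says.** Two sections govern leaving the study. Under section 7, participants "may be withdrawn by the investigator if they fail to present for the second dose of the vaccine or for the first control blood draws"; the same sentence adds a severe adverse effect attributed to dose 1. This is discretionary. Section 8.4 is not: "Subjects cannot continue to be followed in the study if they refuse to complete the vaccination process".

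Section 3.1 replaces these subjects: "Participants will be replaced in case of drop out or failure to receive the second dose of the vaccine", and "Failure to have blood drawn for baseline and/or 4 weeks after vaccination will also warrant replacement".

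Progression is a secondary objective in section 1.1: "To determine the rate of lymphoma progression while receiving BTK inhibitors". Section 5.2 takes it from the treating oncologist's latest assessment, and section 5 says how it is collected. At visit 4, "A chart review will be performed to assess CLL/WM progression on BTK inhibitor therapy". At visit 5, "A last chart review also be performed to assess incidence of zoster reactivation and disease progression". Section 13.2.b tests vaccine response against progression at visits 4 and 5 with Fisher's exact test, and fits a mixed model to the markers at baseline, week 4 and month 24.

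Two provisions keep subjects in. Those who change or stop BTK therapy before dose 2 remain on study (sections 3.1 and 7). Those who receive dose 2 late, but within the 2 to 6 months that section 8.4 cites from the label, can still be included while data collection is ongoing.

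**The concern.** The plan does not distinguish being non-evaluable for the week-4 antibody endpoint from being off study. The first is a sound reason to replace a subject. It is not a reason to stop reading the chart of someone who has been dosed, when the outcome of interest is progression or zoster.

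Replacement does not repair this. It restores the count of 30 by substituting a completer for a non-completer, so the progression rate would describe those who completed both doses and the week-4 draw. If missing a dose or a draw is related to health, that group is selected. Zoster reactivation is not a listed objective, but it is collected at the last chart review, and section 13.2.a names shingles as the primary outcome of the future trial that this pilot is meant to inform.

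**Working it through.** **Which results can be affected.** Setting the withdrawal rules beside what each analysis needs:

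| Subject | Rule | Progression and zoster (chart) | Week-4 response and its test against progression | Month-24 markers and visit-5 test |
|---|---|---|---|---|
| Refuses dose 2 | 8.4, mandatory | Avoidably lost | Unavailable under any follow-up rule | No post-dose-2 result exists |
| Misses dose 2, or is withdrawn before it after a severe adverse effect attributed to dose 1 | 7, discretionary | Avoidably lost if withdrawn | Unavailable under any follow-up rule | No post-dose-2 result exists |
| Two doses, misses visit-4 draw | 7, discretionary | Avoidably lost if withdrawn | Unavailable under any follow-up rule | Avoidably lost if withdrawn |

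Only the last row touches month-24 antibody and cellular results. Section 5.2 defines the month-24 humoral response as antibody above the test threshold at that time, so no week-4 sample is needed. The mixed model can use baseline and month 24 alone.

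**The plan's own figure.** Section 13.1 gives 30 evaluable subjects, 10% drop-out and 33 enrolled. 30 × 1.10 = 33, which reproduces it; 30 / 0.90 = 33.3 would round up to 34. The allowance is therefore 33 − 30 = 3 subjects.

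**Size for the progression rate.** The documents give no progression rate, so the counts of progressions are assumptions. Take all 33 as dosed, 3 lost, and x progressions among the 30 followed.

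- Reported rate: x/30.
- Bounds for all dosed: x/33 if none of the lost progress, (x + 3)/33 if all do.
- x = 2: reported 6.7%; bounds 2/33 = 6.1% and 5/33 = 15.2%.
- x = 3: reported 10.0%; bounds 3/33 = 9.1% and 6/33 = 18.2%.
- x = 5: reported 16.7%; bounds 5/33 = 15.2% and 8/33 = 24.2%.

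The bounds are extremes. If those lost progress k times as often as the 30 followed, the x = 3 case gives (3 + 3 × k × 0.10)/33:

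- k = 2: 3.6/33 = 10.9%.
- k = 3: 3.9/33 = 11.8%.

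The Clopper-Pearson 90% interval for 3/30 is 2.8% to 23.9%, so a shift of 1 to 2 points is small beside sampling error. More losses widen the bounds: with 5 lost and 3/30 observed, they are 3/35 = 8.6% and 8/35 = 22.9%.

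**The case against.** The strongest case on the other side is that the rules bite less than they seem to. Much of it stands.

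- A reader might infer that sections 7 and 8.4 together discard two-dose subjects who miss the visit-4 draw. They do not. Section 8.4 covers only refusal to complete vaccination, and section 7 only permits withdrawal. Its explicit stop on data collection is tied to withdrawal of consent. For withdrawal by the investigator, the text is silent on chart review, and that silence is the gap.
- A reader might infer that the response-progression analysis loses events at both time points. Subjects without a week-4 response cannot enter the week-4 test under any rule. At visit 5 the only recoverable subjects are two-dose subjects who missed the visit-4 draw, were withdrawn, and would have given a sample that Table 1 labels optional.
- No section gives reasons for missed doses or draws, so a link to illness is inferred. Keeping subjects who change or stop BTK therapy before dose 2 already closes one likely route by which progressing patients would be lost. The withdrawal provision for a severe adverse effect is the one health-related route that the text states.
- The 10% allowance also covers laboratory problems (section 13.1), and subjects who withdraw consent stay lost whatever the rule. Three is thus a ceiling within the planned allowance.

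What the objection does not remove is the mandatory bar in section 8.4, or the absence of any chart follow-up for dosed subjects withdrawn under section 7.

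**Conclusion.** The point holds as a minor one. The withdrawal rules can needlessly drop dosed subjects from a stated secondary endpoint and from the zoster count, both of which need only the chart. The primary endpoint and the week-4 response-progression test are not affected. Month-24 marker results and the visit-5 test are affected only through two-dose subjects withdrawn at the investigator's discretion after a missed visit-4 draw.

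With at most 3 of 33 lost and 3/30 progressing, both assumed, the upper bound lies 18.2 − 10.0 = 8.2 points above the reported rate; the two- to threefold scenario moves it by 0.9 to 1.8 points. A reader might conclude that the rate would be about one-third too low. That requires 2 of the 3 lost to progress (5/33 = 15.2%), which is 66.7% against 10.0%, a 6.7-fold higher rate that nothing in the documents supports. Nor is the direction certain, since the lower bound of 9.1% is below the reported 10.0%.

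**What to change.** In sections 7 and 8.4, define two separate states: not evaluable for the week-4 endpoint, which triggers replacement, and withdrawn from the study. Then, unless consent is withdrawn:

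- continue the visit-4 and visit-5 chart reviews for every subject who received a dose;
- report progression and zoster reactivation in all dosed subjects;
- keep two-dose subjects who missed the visit-4 draw for the optional month-24 sample, and include their available visits in the mixed model.

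The cost is protocol wording, about three extra chart reviews per visit, and asking these subjects' permission for the 24-month review, which section 4.2 already requires of all subjects. Some who refused dose 2 may decline. No extra enrolment is needed, and the change concerns data follow-up only, not vaccination or clinical management.

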8. STUDY DRUG/DEVICE/BIOLOGIC ADMINISTRATION/ASSIGNMENT

8.1. Study Drug/Device/Biologic

- Shingrix will be acquired by the outpatient hospital pharmacy. The vaccine is supplied as a single-dose vial of lyophilized varicella zoster virus glycoprotein E (gE) to be reconstituted with the accompanying vial of AS01B adjuvant suspension component. After reconstitution, a single dose of Shingrix is 0.5 mL, to be administered intramuscularly. After reconstitution, each 0.5-mL dose is formulated to contain 50mcg of the recombinant gE antigen, 50mcg of MPL, and 50mcg of QS-21. Each dose also contains 20mg of sucrose (as stabilizer), 4.385mg of sodium chloride, 1mg of DOPC, 0.54mg of potassium dihydrogen phosphate, 0.25mg of cholesterol, 0.160mg of sodium dihydrogen phosphate dihydrate, 0.15mg of disodium phosphate anhydrous, 0.116mg of dipotassium phosphate, and 0.08mg of polysorbate 80. This is not an investigational drug and will be given as standard of care according to the FDA label. The vaccine will be provided for patients enrolled in the study.

8.2. Dosage of Study Drug/Biologic

Dosage of study drug: Shingrix vaccine 50 mcg of anti-gE protein and adjuvant product given at month 0 and month 2.

Should a vaccine-related SAE happen between doses 1 and 2, dose 2 may be omitted. There will be no other dose adjustment.

8.3. Accountability of Investigational Supplies

Vaccines will be obtained and administered through the outpatient hospital pharmacy and kept at that location until reconstitution and administration to the patients. The pharmacist will be responsible for receipt, storage, reconstitution and record keeping.

8.4. Subject Withdrawal of Study Drug

Subjects cannot continue to be followed in the study if they refuse to complete the vaccination process. However, the label of the vaccine specifies the second dose of the vaccine can be administered between 2 to 6 months subsequent to the first one. In that context, if subjects were to get the second dose within that period, they could still be included in the trial, provided data collection is still ongoing.

9. SAFETY AND REPORTABLE EVENTS

9.1. Serious Adverse Event

A serious adverse event is defined as any adverse medical experience that results in any of the following outcomes:

- death;
- is life-threatening;
- requires inpatient hospitalization or prolongation of existing hospitalization;
- results in persistent or significant disability/incapacity;
- is a congenital anomaly/birth defect; or
- requires medical or surgical intervention to prevent permanent impairment or damage.

The following attribution scale will be used:

- Definite: SAE is clearly related to the investigational agent
- Probable: SAE is likely related to the investigational agent
- Possible: SAE is possibly related to the investigational agent
- Unlikely: SAE is doubtfully related to the investigational agent
- Unrelated: SAE is clearly not related to the investigational agent

Serious adverse events, and deaths that occur during the patient's study participation will be recorded in the REDCap database. SAEs will be monitored from the first dose of study vaccine until 4 weeks (28 days) post-last dose of vaccine or withdrawal from participation. All SAEs should be monitored until they are resolved or are clearly determined to be due to a patient's stable or chronic condition or intercurrent illness(es).

9.2. Responsibilities for Reporting Serious Adverse Events

All serious adverse events will be reported in the REDCap database within 5 business days of learning of the event. SAE reports are expected to include sufficient detail so as to determine the severity, toxicity grade, expectedness and treatment. The report should be updated to document resolution or any sequelae. The research team will review these reports and determine if further action is required. We do not expect frequent SAEs in that study. Even in immunocompromised patients, previous studies have shown favorable safety profiles

with the use of that vaccine and no SAEs have been found to be clearly attributed to the vaccine.

